7.6 Pregnancy in the Clinical Study

Women who are pregnant at the time of study entry are excluded from participation. However, pregnancy should be included in the pregnancy eCRF when a woman becomes pregnant during the study. Pregnancy is not reportable as an AE; however, complications may be reportable and will be decided on a case-by-case basis.

[figure not shown]
8 CONFIDENTIALITY, BIAS, AND MASKING

8.1 Subject Confidentiality and Methods Used to Minimize Bias

The investigator must ensure that the subject's anonymity is maintained throughout the course of the study. In particular, the investigator must keep an enrollment log with confidential identifying information that corresponds to the subject numbers and initials of each study participant. All documents submitted to the sponsor will identify the subjects exclusively by number and demographic information. No other personally identifying information should be transmitted to the sponsor.

This study is double-masked with subjects randomized to use Alcon serafilcon A or AOHP contact lens for the duration of 2-week treatment period.

The investigator and sponsor personnel (other than site monitors, clinical operations lead, person responsible for generating the randomization schedule, and unmasked clinical data managers) involved in reporting, obtaining, and/or reviewing the clinical evaluations will be masked to the identity of the contact lens being administered. This level of masking will be maintained throughout the conduct of the study. Unmasking will occur only after all planned study data have been validated, and the database locked.

8.2 Unmasking of the Study Treatment

Masked information on the identity of the assigned medical device should not be disclosed during the study. In the event of a medical emergency where the knowledge of subject treatment is required, individual investigator(s) will have the ability to unmask the treatment assignment for a specific subject. If time allows, the appropriate study sponsor representative should be contacted prior to unmasking. The study sponsor must be informed of all cases in which the code was broken and of the circumstances involved. Additionally, the study sponsor may be required to unmask the information in order to fulfill expedited regulatory reporting requirements.

9 DATA HANDLING AND ADMINISTRATIVE REQUIREMENTS

9.1 Completion of Source Documents and Case Report Forms

The nature and location of all source documents will be identified to ensure that original data required to complete the eCRFs exist and are accessible for verification by the site monitor, and all discrepancies shall be appropriately documented via the query resolution process.

Study monitors are appointed by the study sponsor and are independent of study site staff. If electronic records are maintained, the method of verification must be determined in advance of starting the study.

At a minimum, source documents should include the following information for each subject:

- Subject identification (name, sex, race/ethnicity)
- Documentation of subject eligibility
- Date of informed consent
- Dates of visits
- Documentation that protocol specific procedures were performed
- Results of study parameters, as required by the protocol
- IP accountability records
- Documentation of AEs and other safety parameters (if applicable)
- Records regarding medical histories and the use of concomitant therapies prior to and during the study
- Date of study completion and reason for early discontinuation, if applicable

It is required that the author of an entry in the source documents be identifiable. Direct access to source documentation (medical records) must be allowed for the purpose of verifying that the data recorded on the eCRF are consistent with the original source data.

Only designated individuals may complete the eCRFs. The eCRFs will be submitted at regular intervals following the clinical study visit schedule. It is expected that all data reported will have corresponding entries in the source documents. The principal investigator is responsible for reviewing and certifying that the eCRFs are accurate and complete. The only subject identifiers recorded on the eCRFs will be subject number and subject demographic information.

9.2 Data Review and Clarifications

Upon completion of the eCRFs, a targeted review of the eCRF data to the subject's source data will be completed by the site monitor to ensure completeness and accuracy. Additional data clarifications and/or additions may be needed as a result of the data cleaning process. Data clarifications are documented and are part of each subject's eCRFs.

9.3 Regulatory Documentation and Records Retention

The investigator is required to maintain up-to-date, complete regulatory documentation as indicated by the sponsor and the investigator's files will be reviewed as part of the ongoing study monitoring. Financial disclosure is not subject to regulatory inspection and should be kept separately.

Additionally, the investigator must keep study records and source documents until the sponsor provides written approval for their destruction. If the investigator retires, relocates, or for any other reason withdraws from responsibility of keeping the study records, the sponsor must be notified, and suitable arrangements made for retention of study records and source documents needed to comply with national and international regulations (generally 2 years after discontinuing clinical development or after the last marketing approval).

10 ETHICS AND COMPLIANCE

This trial will be conducted in accordance with the ethical principles that have their origin in the Declaration of Helsinki and the referenced directives, regulations, guidelines, and/or standards.

10.1 Compliance

[figure not shown]
The investigator must ensure that all personnel involved in the conduct of the study are qualified to perform their assigned responsibilities through relevant education, training, and experience. The investigator and all clinical study staff must conduct the clinical study in compliance with the protocol. Deviations from this protocol, regulatory requirements, and/or GCP must be recorded and reported to the sponsor prior to database lock. If needed, corrective and preventive action should be identified, implemented, and documented within the study records.

10.2 Institutional Review Board (IRB)

This trial requires IRB approval prior to initiation. This protocol, subject informed consent, and subsequent amendments will be reviewed and approved by an IRB.

Before clinical study initiation, this protocol, the ICF (and assent form, if applicable), any other written information given to subjects, and any advertisements planned for subject recruitment must be approved by an IRB. The investigator must provide documentation of the IRB approval to the study sponsor. The approval must be dated and must identify the applicable protocol, amendments (if any), ICF, assent form (if any), all applicable recruiting materials, written information for subject, and subject compensation programs. The IRB must be provided with a copy of the Investigator's Brochure, any periodic safety updates, and all other information as required by local regulation and/or the IRB. At the end of the study, the investigator must notify the IRB about the study's completion. The IRB also must be notified if the study is terminated prematurely. Finally, the investigator must report to the IRB on the progress of the study at intervals stipulated by the IRB.

Voluntary informed consent must be obtained from every subject (and/or legal representative, as applicable) prior to the initiation of any screening or other study-related procedures. The investigator must have a defined process for obtaining consent. Specifically, the investigator, or delegate, must explain the clinical study to each potential subject and the subject must indicate voluntary consent by signing and dating the approved informed consent form. The subject must be provided an opportunity to ask questions of the investigator, and if required by local regulation, other qualified personnel. The investigator must provide the subject with a copy of the consent form written in a language the subject understands. The consent document must meet all applicable local laws and provide subjects with information regarding the purpose, procedures, requirements, and restrictions of the study, along with any known risks and potential benefits associated with the IP, the available compensation, and the established provisions for maintaining confidentiality of personal, protected health information. Subjects will be told about the voluntary nature of participation in the study and must be provided with contact information for the appropriate individuals should questions or concerns arise during the study. The subject also must be told that their records may be accessed by appropriate authorities and sponsor-designated personnel. The investigator must keep the original, signed copy of the consent and must provide a duplicate copy to each subject according to local regulations. Following this study, the subject will return to their eye care professional for their routine eye care and contact lenses.

13 APPENDIX

Not applicable.

1 STUDY OBJECTIVES AND DESIGN

1.1 Study Objectives

PRIMARY OBJECTIVE

The objective of this study is to assess the clinical performance of two reusable silicone hydrogel contact lenses when worn on a daily wear modality.

1.2 Study Description

Key components of the study are summarized in Table 1-1.

Table 1-1 **Study Description Summary**

Study Design	Prospective, randomized, bilateral crossover, double-masked
Study Population	Volunteer subjects aged 18 or over who are habitual spherical soft contact lens wearers (excluding current/previous ACUVUE OASYS® 2 Week with HYDRACLEAR® PLUS (AOHP) habitual lens wearers and daily disposable lens wearers), have at least 3 months of contact lens wearing experience, and who wear their habitual lenses at least 5 days per week and at least 8 hours per day. [REDACTED] [REDACTED] [REDACTED] [REDACTED] [REDACTED] Target to complete: 60 Planned to enroll: ~68
Number of Sites	~5 US
Test Product(s)	Alcon serafilcon A contact lenses (serafilcon A; LID022821)
Comparator Product(s)	ACUVUE OASYS® 2 Week with HYDRACLEAR® PLUS (AOHP; senofilcon A)
Planned Duration of Exposure	~28 days total duration (test and comparator) plus wash-out: Test Product: ~14 days Comparator Product: ~14 days
Visits	Prescreening (optional) Visit 1 – Screening/Baseline Visit 2 – Dispense Lens 1 [2 (at least 48 hours) - 4 days after Visit 1*]

	
Visit 3 – Week 1 Follow-up Lens 1 [7 -0/+1 days after Visit 2] Visit 4 – Week 2 Follow-up Lens 1 [7 -0/+1 days after Visit 3] Visit 5 – Dispense Lens 2 [2 (at least 48 hours) - 4 days after Visit 4*] Visit 6 – Week 1 Follow-up Lens 2 [7 -0/+1 days after Visit 5] Visit 7 – Week 2 Follow-up Lens 2/Exit [7 -0/+1 days after Visit 6]
 
* Washout period with habitual spectacles only after Visit 1 and after Visit 4

--	--

1.3 Randomization

A member of the Randomization Programming group at Alcon who is not part of the study team will generate the randomized allocation schedule(s) for study lens sequence assignment. Randomization will be implemented in the Electronic Data Capture (EDC)/randomization integration system.

Subjects will be randomized in a 1:1 manner to receive treatment (lens) in crossover sequence as follows:

Sequence	EDC/randomization integration system	Lens Name
Sequence 1	LID022821/AOHP	Alcon serafilcon A/AOHP
Sequence 2	AOHP/LID022821	AOHP/Alcon serafilcon A

1.4 Masking

This study is double-masked.

1.5 Interim Analysis

There are no plans to conduct an interim analysis, and no criteria by which the study would be terminated early based upon statistical determination.

2 ANALYSIS SETS

2.1 Safety Analysis Set

Safety analyses will be conducted using the safety analysis set on a treatment-emergent basis. As such, the safety analysis set will include all subjects/eyes exposed to any study lenses evaluated in this study, [REDACTED]

For treatment-emergent safety analyses, subjects/eyes will be categorized under the actual study lenses exposed in the corresponding lens sequence.

Adverse events occurring from the time of informed consent but prior to first exposure to study lenses will be summarized in subject listings.

3 SUBJECT CHARACTERISTICS AND STUDY CONDUCT SUMMARIES

The following tables will be presented:

- Subject Disposition by Lens Sequence
- Analysis Set by Lens
- Analysis Set by Lens Sequence
- Subject Accounting by Lens Sequence
- Demographics by Lens Sequence
- Baseline Characteristics by Lens Sequence [lens brand; lens power; lens solution; habitual lens wear and rewetting drop usage, best corrected visual acuity; keratometry readings]

In addition, the following subject listings will be provided:

- Listing of Subjects Excluded from Protocol Defined Analysis Set
- Listing of Lens Sequence Assignment by Investigator
- Listing of Subjects Discontinued from Study

4 EFFECTIVENESS ANALYSIS STRATEGY

This study defines 1 primary [REDACTED] effectiveness endpoint. The Safety Analysis Set will be used for all effectiveness analyses.

Select effectiveness endpoints will also be summarized by period.

Continuous variables will be summarized using the number of observations, mean, standard deviation, median, minimum, and maximum. Categorical variables will be summarized with frequencies and percentages from each category.

[figure not shown]
All data obtained in evaluable subjects/eyes will be included in the analysis. No imputation for missing values will be carried out.

A listing of select effectiveness data will also be provided.

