6.1 Subject Evaluability

The final subject evaluability will be determined prior to breaking of the code for masked treatment (lens) sequence assignment and locking the database, based on the Deviations and Evaluability Plan.

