6.2 Analysis Data Sets

6.2.1 Safety Analysis Set

Safety analyses will be conducted using the safety analysis set on a treatment-emergent basis. As such, the safety analysis set will include all subjects/eyes exposed to any study lenses evaluated in this study. [REDACTED]

[REDACTED] For treatment-emergent safety analyses, subjects/eyes will be categorized under the actual study lenses exposed in the corresponding lens sequence.

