4.2 Effectiveness Hypotheses

Primary Effectiveness

No inferences are to be made on the primary effectiveness endpoint; therefore, no hypotheses are formulated.

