7 SAMPLE SIZE AND POWER CALCULATIONS

No formal sample size calculation is provided given the descriptive nature of the study.

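### Does the word *evaluable* leave the primary visual acuity table with two competing analysis populations?

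*SAP*

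**What the plan says.** On the population, SAP Section 4 is explicit: "The Safety Analysis Set will be used for all effectiveness analyses". Protocol 6.4 says the same. The set is defined in Protocol 6.2.1, where "the safety analysis set will include all subjects/eyes exposed to any study lenses evaluated in this study"; SAP 2.1 uses the same words. In both places redacted text follows directly, and in the SAP it falls within the defining sentence.

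A later paragraph of SAP Section 4 says that "All data obtained in evaluable subjects/eyes will be included in the analysis" and then rules out imputation. Protocol 6.6, headed as the section on missing data, carries the same pair of sentences.

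Protocol 6.1 governs evaluability: "The final subject evaluability will be determined prior to breaking of the code for masked treatment (lens) sequence assignment and locking the database", and this is done "based on the Deviations and Evaluability Plan". That plan is not among the public documents. No visible text defines *evaluable*, links it to the Safety Analysis Set or sets up a second analysis set. SAP Section 3 plans a "Listing of Subjects Excluded from Protocol Defined Analysis Set".

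**The concern.** Exposure and evaluability look like different criteria. Exposure is a fact of dispensing and wear. Evaluability, going by the title of the plan that decides it, may depend on protocol deviations. An exposed subject judged non-evaluable would then be in the primary table under one sentence and apparently outside it under the other.

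In a lens-wear study this could matter. Protocol 4.1 asks for wear on every day and for at least 10 hours a day. A subject who sees poorly or is uncomfortable may fall short because of the lens. Excluding such subjects or eyes would favour those doing well. Excluding one lens period but not the other would leave the two lens summaries resting on different people. The reported N and mean would then depend on which sentence the programmer followed.

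**Working it through.** The plan gives no figure to reproduce: it has no power calculation, margin or assumed standard deviation. The check is a comparison of texts, followed by a sense of scale.

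**Texts side by side**

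1. *Which sentence names the population?* Only the one assigning the Safety Analysis Set to all effectiveness analyses. The *evaluable* sentence says what will be included. It does not say *only*, and it gives no instruction to exclude.
2. *What is the* evaluable *sentence for?* In the protocol it sits under missing data, and in both documents the ban on imputation comes next. It reads naturally as: use what was observed and fill nothing in.
3. *How many sets are defined?* One in each document. The exclusions listing in SAP Section 3 also refers to a single protocol-defined set. No per-protocol set exists for an evaluability rule to create, so *evaluable* may simply mean belonging to the one set.
4. *Does the set rest on exposure alone?* This cannot be established, because redacted text follows the definition. It may qualify the set or supply the link to evaluability.
5. *Are exclusions for short wear or missed days planned?* No visible text says so. The criteria are in a plan that is not available here.
6. *Are the safety tables affected?* SAP 5.3 ties all safety analyses to the set in SAP 2.1. In the SAP the *evaluable* sentence appears only in the effectiveness section.

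**Scale, with assumed inputs**

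Suppose k of n subjects are dropped and their mean acuity is worse than that of the rest by d. The lens mean then shifts by (k/n) × d. Take n = 68, the planned enrolment in the Protocol Synopsis and SAP Table 1-1. The documents give neither k nor d.

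| k | d (logMAR) | Shift in lens mean (logMAR) |
|---|---|---|
| 1 | 0.10 | 1/68 × 0.10 = 0.0015 |
| 3 | 0.10 | 3/68 × 0.10 = 0.0044 |
| 7 | 0.10 | 7/68 × 0.10 = 0.0103 |
| 8 | 0.20 | 8/68 × 0.20 = 0.0235 |

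The number exposed may be below 68. With n = 60, the target to complete, the middle rows become 3/60 × 0.10 = 0.0050 and 7/60 × 0.10 = 0.0117.

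If both eyes and both periods were lost, N for each lens would fall by 3 to 7 subjects, or 6 to 14 eyes. If losses fell on one lens only, the whole shift would appear in the difference between the two lens means. The visible plan does not analyse that difference.

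**Use of the result**

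SAP 4.2 states: "No inferences are to be made on the primary effectiveness endpoint; therefore, no hypotheses are formulated". SAP Section 7 adds: "No formal sample size calculation is provided given the descriptive nature of the study". The SAP executive summary says that decision criteria for success do not apply. A shift in the descriptive mean would change no test, error rate or decision rule.

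**The case for a change.** The best argument for an edit is that the word must either do something or do nothing. Knowing who was exposed needs no masked determination at the end of the study and no deviations plan. If evaluability has an effect beyond exposure, the two sentences are unreconciled; if it has none, the word is redundant. Fixing evaluability before the code is broken prevents deliberate selection by lens, but not selection that arises because a lens itself causes deviations. The lenses also have different replacement periods (about 7 and about 14 days), so types of deviation could differ between them. The wording permits decisions at eye level, and replacing a phrase in two sentences costs almost nothing.

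Two parts of this stand: the term is undefined in the visible text, and masking is only a partial safeguard. The rest depends on exclusions that no document describes, under a plan nobody outside the sponsor can read here, and next to a definition whose remainder is blacked out. Rewriting the sentence would amount to re-scoping that unseen plan. A departure from the named set would also leave traces. SAP Section 4 reports the number of observations with each continuous summary, and SAP Section 3 provides tables of the analysis set by lens and by sequence, besides the exclusions listing. A reader could compare these counts, allowing for missed visits.

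**Conclusion.** No change is needed. The documents leave *evaluable* undefined, and that is a real but small gap in wording. It does not create two incompatible populations, because the population is named outright, only one set is defined, and the later sentence concerns observed data and non-imputation. An analyst following the explicit statement would summarise observed Week 1 acuity in the Safety Analysis Set, which is sound for this descriptive study. Under the alternative reading, the movement in a lens mean is about 0.004 to 0.010 logMAR for 3 to 7 of 68 subjects at an assumed 0.10 logMAR deficit, and 0.0235 in the most extreme case tabulated.

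The conclusion rests on taking the population statement at face value and on the absence of any visible exclusion rule. It would need another look if the Deviations and Evaluability Plan, or the redacted part of the set definition, removed exposed subjects or eyes for reasons that a lens could cause.

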4.1 Effectiveness Endpoints

Primary Effectiveness Endpoint

[figure not shown]
The primary effectiveness endpoint is visual acuity (VA) with study lenses at Week 1 Follow-Up, collected at distance for each eye in logMAR.

4.2 Effectiveness Hypotheses

Primary Effectiveness

No inferences are to be made on the primary effectiveness endpoint; therefore, no hypotheses are formulated.

4.3 Statistical Methods for Effectiveness Analyses

Primary Effectiveness

Descriptive statistics will be provided, at each visit. Summary by period will also be generated.

4.4 Multiplicity Strategy

No multiplicity adjustment needs to be considered for the effectiveness endpoints since no formal hypothesis testing will be conducted.

4.5 Subgroup Analyses and Effect of Baseline Factors

It is not expected that demographics or baseline characteristics will have an impact on the study results in this study. No subgroup analyses are planned.

4.6 Interim Analysis for Effectiveness

No interim analysis is planned for effectiveness endpoints.

5 SAFETY ANALYSIS STRATEGY

The focus of the safety analysis will be a comprehensive descriptive assessment of occurrence of adverse events as well as the other listed parameters. Therefore, no inferential testing will be done for the safety analysis.

5.1 Safety Endpoints

The safety endpoints are

- Adverse events (AE)
- Biomicroscopy Findings
 - Limbal hyperemia

- Bulbar hyperemia
- Corneal staining
- Conjunctival staining
- Palpebral conjunctival observations
- Corneal epithelial edema
- Corneal stromal edema
- Corneal vascularization
- Conjunctival compression/indentation
- Chemosis
- Corneal infiltrates
- Other findings
- Device deficiencies

5.2 Safety Hypotheses

There are no formal safety hypotheses in this study. The focus of the safety analysis will be a comprehensive descriptive assessment of safety endpoints listed in Section 5.1.

